Title: A remote postpartum blood pressure surveillance and reminder system for hypertensive disorders of pregnancy: a randomized clinical trial**Applicant:** [name]**Attending Principal Investigator:** [name]**1. Proposal abstract**

The overarching goals of our study are to (i) assess whether implementation of a Bluetooth-enabled remote blood pressure monitoring system improves monitoring of women with hypertensive disorders of pregnancy (HDP) in the postpartum period, (ii) assess whether improved monitoring improves blood pressure control and reduces morbidity in this patient population and (iii) evaluate the factors associated with poor postpartum follow up among patients with HDP. HDP, an umbrella term which includes chronic hypertension with or without superimposed preeclampsia, gestational hypertension, preeclampsia with or without severe features, HELLP syndrome and eclampsia, affect nearly 10% of pregnancies and are some of the most common conditions encountered by obstetricians.¹ In the postpartum period, hypertension can be related to persistence of pre-existing HDP, or it can develop de novo postpartum.² HDP are an important cause of maternal morbidity and mortality, and a leading cause of postpartum readmission.³ Therefore, the American College of Obstetricians and Gynecologists (ACOG) recommends that in women with HDP, blood pressure should be monitored inpatient or with equivalent outpatient surveillance for at least 72 hours postpartum and again at 7-10 days after delivery.¹ The majority of patients, however, are discharged on postpartum day 2 or 3, often prior to this 72-hour mark and almost always prior to the 7-10 day mark. Even if they are discharged home with a plan for outpatient surveillance and follow-up, postpartum follow-up rates are known to be low: in one secondary analysis of postpartum follow-up and persistent hypertension in women with severe preeclampsia, the 6-week follow-up rate was 52%. Of those patients who did follow up, 21% had persistent hypertension.⁴ With low-follow up rates and high rates of persistent hypertension in those that do follow up, clearly there is a large subset of women with continued hypertension who are simply lost to care. Barriers to care for women in the postpartum period include lack of consistent provider, lack of understanding of discharge instructions and difficulties with transportation. Additionally, many women have difficulty managing their own health issues when also taking care of a newborn.⁵ Therefore, a proactive approach to monitoring BP as an outpatient in the postpartum period that involves minimal patient burden is needed to identify women with poorly controlled BP, adjust antihypertensive medications, and prevent hypertension-associated morbidity.

Remote blood pressure monitoring offers a possible solution to this problem. In a randomized control trial design, we propose to use a Philips Remote Patient Monitoring (RPM) System to assess whether we can improve blood pressure monitoring during this critical period. RPM has been shown repeatedly in the non-obstetric literature to improve hypertension management by increasing the amount of patients' involvement in their own care, and providing physicians with more dynamic control of patients' blood pressure.⁶ We hypothesize that a Bluetooth-enabled blood pressure monitoring system will lead to closer monitoring and improved communication

between patients and their providers. Ultimately, we hypothesize that this will lead to earlier initiation and more active titration of anti-hypertensive medications, earlier recognition of and intervention for women at risk of significant hypertension-related morbidity and decreased rates of maternal morbidity and mortality.

2. Proposal body

2.1 Background

There is a paucity of data on the diagnosis and management of HDP in the postpartum period. The natural history of postpartum HDP is poorly understood, and estimates of the prevalence of the disease vary widely, ranging from 0.3 to 27.5%.⁷ In older studies of patients who had planned postpartum inpatient stays of 1 week or longer, 12% of previously normotensive women became hypertensive and >50% of women with HDP had a systolic/diastolic BP \geq 150/100 mmHg.^{8,9} Since those studies were performed, the length of a hospital admission for delivery has shortened. Most women are now discharged within 48-72 hours of delivery, and many are not evaluated again until their traditional 6-week postpartum visit. However, nearly 20% of women who deliver a baby in the United States will be seen and discharged from an emergency department prior to their traditional 6-week postpartum visit, and an additional 1-2% of patients will be admitted.¹⁰ In a 2016 study, hypertension was found to be the second most common cause of postpartum readmission in the United States, after infection.¹¹ Short-term complications that are known to occur secondary to uncontrolled HDP include stroke, seizure, pulmonary edema, posterior reversible encephalopathy syndrome, renal or hepatic dysfunction, and death.¹² HDP is also a risk factor for the long-term development of cardiovascular disease, hypertension, stroke and renal disease.¹³ Given all of these associated short- and long-term morbidities, close follow up of women with HDP is essential in the postpartum period and beyond. Yet due to the scarceness of empiric data on postpartum BP, there are limited recommendations regarding the initiation, frequency, and duration of postpartum BP monitoring in women with HDP.¹⁴

ACOG guidelines recommend that in women with HDP, blood pressure should be monitored in the hospital or with equivalent outpatient surveillance for at least 72 hours postpartum and again 7-10 days after delivery, or earlier in women with symptoms.¹ At CUIMC, the usual care for discharge of patients with HDP at CUIMC involves the following (hereafter referred to as “usual care”):

1. A prescription for a blood pressure cuff and instructions to measure blood pressures twice daily at home. *No make or model is specified, and the patient is responsible for obtaining the device from a pharmacy.*
2. Arrangements for a nursing service to visit the patient’s home for a blood pressure check within the first few days after discharge. *The exact timing of this is not standardized; for example, if the patient is discharged on Friday, the nurse may come 72 hours later on Monday; if the patient is discharged on Thursday, the nurse may come 24 hours later on Friday.*
3. An appointment for a blood pressure check in the clinic where the patient received prenatal care at 7-10 days postpartum; the patient is instructed to bring logs of their twice daily blood pressure measurements to this visit. *Patients with private insurance are told to make this appointment with their prenatal care provider but are not given the*

appointment prior to discharge. Patients who are discharged on or after 7 days postpartum are told to follow up in one week

4. *An appointment for a 6-week postpartum visit. Patients with private insurance are told to make this appointment with their prenatal care provider but are not given the appointment prior to discharge.*

If followed in full by the patient, these policies do follow the current guidelines set forth by ACOG. However, extrapolating from the limited published data regarding follow-up rates and from approximations from our own publicly-insured population, it is reasonable to presume that only about half of these patients present for their one-week blood pressure check appointment.¹⁵ Poor follow-up is not a problem unique to our institution. In a secondary analysis of factors associated with postpartum follow-up and persistent hypertension in women with severe preeclampsia by Levine et al, the 6-week follow-up rate was 52%. Among those with 6-week follow-up, 21% had persistent hypertension.⁴ With low-follow up rates and high rates of persistent hypertension in those that do follow up, clearly there is a large subset of women with continued hypertension who are simply lost to care. Barriers to care in the postpartum period include lack of a consistent provider, lack of understanding of discharge instructions whether due to poor health literacy, a language difference or a failure of the provider to properly explain instructions, and difficulties with transportation. Additionally, many women have difficulty managing their own health issues when also taking care of a newborn, possibly with limited support.¹⁶

Postpartum care in general in the United States leaves something to be desired, and has been the subject of many studies aiming to determine how we can improve delivery of care to these patients.¹⁷ In May of 2018, citing the urgent need to reduce severe maternal morbidity and mortality in the United States, ACOG released a committee opinion on the “fourth trimester,” referring to the critical but oft-neglected postpartum period. It proposes a restructuring of postpartum care from a single visit at the 6-week mark to an ongoing process with services and support tailored to each woman’s individual needs. Women with HDP should have blood pressure evaluation within 7-10 days postpartum, and women with severe hypertension should be seen within 72 hours.¹⁸ Blood pressure assessment in this time period is critical, as more than 50% of postpartum strokes occur within 10 days of discharge.¹⁹ Early identification and treatment of women with poorly controlled HDP could meaningfully reduce the hypertension-associated morbidity and mortality in this population.

Mobile health technologies have been shown to be useful, both in improving outcomes and in improving patient connectedness to care, both in obstetrics and in other disciplines.^{20,21} In the non-obstetric population, RPM has been shown to improve treatment of hypertension.⁶ RPM has also been studied in pregnancy and the postpartum period in limited contexts. In one such study, where patients self-selected into an RPM program for blood pressure monitoring postpartum, RPM patients reported fewer perceived barriers to care than their usual-care counterparts.²² In another, women randomized to text-based reminders to check blood pressures had a significantly higher rate of recorded blood pressure readings in the first ten days postpartum compared to those randomized to an in-office blood pressure check.¹⁵ Studies such as these are scarce, and there remains a lack of good-quality evidence on the usefulness and efficacy of RPM in patients with HDP.

Our study proposes that the use of mobile health technology, specifically a Bluetooth-enabled blood pressure cuff, will improve the care of women with hypertension in the postpartum period by increasing the amount of blood pressure data collected in the outpatient setting. Increased data and closer surveillance will allow for more active titration of anti-hypertensive medications and assessment of symptoms. We also propose that patients will feel more involved in and connected to their care using RPM.

2.2 Specific aims

Our objective is to trial RPM in the postpartum hypertensive population in a randomized control design, with an aim to increase the number of blood pressure measurements taken during the fragile and under-monitored postpartum period and to thereby improve postpartum blood pressure control and reduce severe morbidity and mortality.

Specific Aim 1. To compare the number of blood pressures recorded in the first 10 days postpartum between patients who have been enrolled in an RPM trial to those who are being treated with the usual care. We hypothesize that women using RPM will have more blood pressure values recorded at outpatient blood pressure assessment compared with patients using the usual care.

- **Sub-aim 1: To compare the percentage of elevated blood pressures that are discussed with an obstetric care provider between patients who have been enrolled in an RPM trial to those who are being treated with the usual care.** We hypothesize that women using RPM will communicate more frequently with their providers regarding elevated blood pressure values.
- **Sub-aim 2: To examine the effect of RPM on blood pressure control at 6 weeks in women with HDP.** We hypothesize that more women using RPM will be normotensive, defined as blood pressure < 140/90 mm Hg, at the end of the postpartum period, compared to those randomized to usual care.

Sub-aim 3: To compare time to outpatient initiation or adjustment of antihypertensive medications in women using RPM compared to the usual care. We hypothesize that women using RPM will have shorter time to initiation of medications or shorter time to change in medication regimen in the outpatient setting than those using the usual care.

Specific Aim 2. To compare rates of compliance with follow up visits between patients who have been enrolled in an RPM trial to those who are being treated with the usual care. We hypothesize that women using RPM will have a higher rate of compliance with outpatient blood pressure assessments and postpartum visits than patients using the usual care

- **Sub-aim 1: To analyze factors associated with poor postpartum follow up in both the study group and the control group.** We hypothesize that factors such as socioeconomic status, wait times at the office or clinic where care is provided, number of children at home, and educational level will be associated with lower follow-up rates.

Specific Aim 3. To assess the ease of use and satisfaction for RPM. We hypothesize that women who use RPM will be satisfied with this method of blood pressure monitoring, and will

feel overall more connected to their care and to their providers than women who receive the usual care.

2.3. Methods

2.3.1 Study Design

This will be a randomized control trial, in which women with HDP diagnosed prior to delivery will be assigned to either usual care or to a telehealth kit that, supplied by Philips. New York Presbyterian has a contract in place with Philips (attached separately to this IRB application under “Philips Contract 5.30”) which allows the hospital to utilize Philips telehealth programs for its patients. The telehealth kit will include a Bluetooth-enabled blood pressure cuff which is FDA approved to monitor blood pressure as well as pulse, and a tablet that includes a clinical monitoring software (eCareCoordinator, or eCC). Further details regarding the devices are outlined in the “Equipment and Software” section below.

Patients will be recruited from the postpartum service. All patients will be asked to check their blood pressure twice per day, once in the morning and once in the evening. Pulse will also be recorded as it is taken automatically at time of blood pressure reading; though this parameter is not being studied, there will be protocols in place to address abnormal values. Control group patients will use the blood pressure cuff that they procure after discharge using the prescription they are given, and will be asked to keep a log of their blood pressure measurements. Study group patients will use the Philips Bluetooth-enabled blood pressure cuff, which will transmit blood pressure measurements via Bluetooth from the monitor to the eCC. These patients will be educated on the use of and enrolled in the software by Philips representatives (via telephone) and research investigators who have been in-serviced on the devices prior to discharge. The tablets are cellular-enabled, so no wireless connection is needed in the patient’s home.

Measurements and surveys for patients in the study group will be scheduled in the eCC (see “HDP Calendar and Intervention Rules,” attached as a separate document to this IRB application). Data for patients in the study group will be transmitted to the Philips Clinical Call Center, staffed daily by nurses from 8am-8pm. The nurses will review measurements and survey results within 2 hours when they are flagged as high for attention. Criteria for flagging and therefore review by a nurse as well as for escalation to an obstetric provider is outlined in the workflow attached as separate documents to this IRB (“HDP calendar and intervention rules” / “Workflows”). If a measurement is flagged as high, the nurse will contact the patient and the patient’s provider (if the patient has not) by phone. The patient will also be automatically instructed via the system to call their provider immediately. If a measurement is flagged as low, the nurse will email the patient’s provider with a summary of the day’s measurements at the end of the day. If a patient does not enter measurements, the nurse will contact the patient directly. If the patient does not enter measurements for 3 consecutive days, the nurse will contact the patient’s provider, and will continue attempting to contact the patient daily. If a nurse cannot get in touch with the patient, the nurse will contact the patient’s provider. If a survey answer is flagged, the nurse will contact the patient and the patient’s provider (if the patient has not) by phone. The patient will also be automatically instructed via the system to call their provider immediately. If the patient does not answer a survey, the nurse will contact the patient the

following day. For all patients, regardless of whether or not they have flagged values, a weekly report of measurements will be generated and sent to the patient's providers every week.

Patients in both groups will be given an appointment to follow-up with their obstetric provider in the office at 7-10 days postpartum. Control group patients will be asked to bring a log of their recorded blood pressures to this visit. The number of measurements *total* and the number of measurements that were *elevated* will be ascertained for each group at this visit.

Patients in the study group will also be prompted to answer a daily survey within the Philips application regarding symptoms of preeclampsia, a weekly survey regarding their medications and satisfaction surveys prior to and at the conclusion of the study period. Patients in the control group will also be given satisfaction surveys prior to and at the conclusion of the study period.

Patients in both groups will be followed from recruitment until the date of their postpartum visit.

Flowcharts illustrating the above work flows can be found in separate attachments to this IRB application ("HDP calendar and intervention rules" / "Workflows").

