- Surveys (p.86-89): describes how surveys are displayed as part of the calendar and how they can be accessed. The surveys that will be available as part of this study are attached as a separate document to this IRB application (“Surveys”). They include:
 - Preeclampsia Symptom Survey-scheduled
 - Preeclampsia Symptoms Survey-reflexive, high acuity
 - Preeclampsia Symptoms Survey-reflexive, low acuity
 - Medication Survey
 - Satisfaction Survey-Program Start (*will also be given to the control group*)
 - Satisfaction Survey-Program End (*will also be given to the control group*)
 - Telemedicine Survey Specific-Program End
- Measurements (p.91-92): describes how patient measurements are displayed and scheduled. **For this study, only blood pressure and heart rate will be measured.**
- Patient issues (p.128-137): describes how acute conditions that affect daily patient care activities are monitored and how chronic problems are tracked.
- Reviewing flags and issues (p.142-146): describes how patients are flagged for clinical assessment and intervention, and how these flags and issues are reviewed and addressed
- Intervention rules (p.188- 210): conditional statements that consist of a condition and an action that the system will trigger when the condition is met. **The intervention rules for this study are attached to the IRB application as a separate document (“HDP calendar and intervention rules”) and workflows can be found as a separate document as well (“Workflows”).**

At the conclusion of the 6-week study period (in other words, after the scheduled postpartum visit or the time when that visit was supposed to occur, if the patient did not present), the patient

will be expected to return the kit. The full patient terms of use are attached to this IRB application as a separate document (“Philips Terms of Use”).

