2.3.6 Outcomes

- 1) **Primary outcome:** Our primary outcome will be percentage of the recommended twice daily blood pressures reported between hospital discharge and outpatient blood pressure assessment.
- 2) **Secondary outcomes:** Secondary outcomes will include:
 1. Percentage of recorded blood pressure values during that time frame that are elevated (>140 systolic OR >90 diastolic)
 2. Percentage of elevated blood pressures that triggered a phone call to an obstetric provider
 3. Rate of attendance at outpatient blood pressure assessment
 4. Incidence of elevated blood pressure at the outpatient blood pressure assessment
 5. Rate of outpatient assessment for postpartum care
 6. Incidence of elevated blood pressure at the postpartum assessment
 7. Time to initiation of antihypertensive medications (in patients who were not on medications at time of discharge) and adjustment of antihypertensive medications
 8. Final dosage of antihypertensive medications at 6 weeks postpartum
 9. Readmission rate
 10. Rate of emergency department visits
 11. Rate of HDP-associated morbidities (e.g.: stroke, seizure, PRES)
 12. Percentage of patients who require a referral to primary care physicians after being discharged from obstetric care at the postpartum visit
 13. Patient satisfaction with the method, to be assessed via a validated clinical survey (attached separately in the document entitled “Surveys”).

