2.4.2 Statistical analysis

For analysis of discrete (categorical) data in independent samples, the Chi-squared test or Fisher exact probability test will be utilized. For group comparisons, continuous data that satisfy the assumptions of normality and homoscedasticity (homogeneity of variance) will be analyzed by t-test (for 2 independent samples) or analysis of variance (>2 groups, ANOVA) with post hoc comparisons by Scheffe tests. When possible, continuous data that do not fulfill the aforementioned assumptions will be mathematically transformed (e.g., logarithmic transformation) before performing t-tests or ANOVA. In some cases, data that do not satisfy these assumptions will be analyzed by nonparametric methods [Mann-Whitney U Test (for two independent samples) or Kruskal-Wallis One-Way ANOVA (for more than two independent

samples)]. Significant Kruskal-Wallis ANOVAs will be followed by Dunn tests for post hoc analysis. The degree of linear association between variables will be measured by the Pearson product moment correlation coefficient or the Spearman rank-order correlation coefficient and their corresponding tests of significance. Multivariate linear or logistic regression will be utilized where appropriate. In all cases, statistical significance will be assumed when $p < 0.05$. Propensity score analysis will be used as a balancing score as deemed necessary.

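### Both arms are given start and end satisfaction surveys, but the plan gives the start survey no role in the analysis, so the Aim 3 comparison may give up precision.

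*Combined protocol and SAP*

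**What the plan says.** Aim 3 in section 2.2 reads "Specific Aim 3. To assess the ease of use and satisfaction for RPM". Its hypothesis also compares the arms: women using remote monitoring are expected to feel more connected to their care and providers than women under usual care. Section 2.3.6 lists the matching endpoint as secondary outcome 13: "Patient satisfaction with the method, to be assessed via a validated clinical survey". It defines no score, scale, time point or change measure.

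On data collection, section 2.3.1 says the study arm will answer "a weekly survey regarding their medications and satisfaction surveys prior to and at the conclusion of the study period", and then "Patients in the control group will also be given satisfaction surveys prior to and at the conclusion of the study period". Section 2.3.5 lists a Program Start and a Program End satisfaction form, each marked as also going to the control group. Their content is in a separate attachment.

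On analysis, section 2.4.2 is a general menu. Categorical data get a chi-squared or Fisher test. Continuous data meeting the usual assumptions "will be analyzed by t-test (for 2 independent samples"), with Mann-Whitney as the nonparametric alternative. Then: "Multivariate linear or logistic regression will be utilized where appropriate". No test is assigned to satisfaction or to Aim 3. Section 2.4.1 inflates the sample size partly to allow for adjustment for confounders, which it does not name.

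**The concern.** A start measure is planned in both arms and no analytic use is stated for it. Women are likely to differ in how satisfied and connected they feel before follow-up begins. If the start and end answers are related, an end-only comparison leaves that variation in the error term and widens the confidence interval. It also makes no correction for whatever chance difference between the arms was present at the start.

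The silence also leaves a choice open. An end-only comparison, a change score and a baseline-adjusted model would all fit within section 2.4.2. They differ in precision, and the choice could be made after the data are seen. No sample size or power was set for satisfaction, so any precision already available is worth using.

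**Working it through.** **1. The plan's own figure.** The only sample size concerns the primary outcome (section 2.4.1: 60% versus 80%, 80% power). With two-sided alpha 0.05 (sidedness is not stated, so this is assumed) and pooled variance:

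n = [1.96 × √(2 × 0.7 × 0.3) + 0.842 × √(0.6 × 0.4 + 0.8 × 0.2)]² / 0.2² = 81.2 per group.

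This reproduces the stated 81. Then 81 × 1.25 = 101.25, stated as 101, and 2 × 101 = 202, later raised to 220. These figures do not bear on satisfaction. They are used here only for arm size: 220 / 2 = 110 per arm, assuming equal allocation and complete surveys.

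**2. Effect of adjustment.** Let σ be the SD of the end score, r the within-arm correlation between start and end scores (assumed equal in both arms), and n the number per arm.

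- Unadjusted variance of the arm difference: 2σ²/n
- Variance adjusted for the start score: 2σ²(1 − r²)/n
- Ratio: 1 − r²
- Equivalent unadjusted size per arm: n / (1 − r²)
- Detectable difference in SD units, two-sided 0.05 and 80% power: (1.960 + 0.842) × √(2/n) × √(1 − r²)

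The documents give neither σ nor r, so results are in SD units over an assumed range of r. The change-score column is the variance of a change-score analysis relative to end-only, 2(1 − r), assuming equal SDs at start and end.

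| Assumed r | Variance factor 1 − r² | Variance cut | SE cut | Equivalent n per arm (from 110) | Detectable difference, 110 per arm | Detectable difference, 81 per arm | Change-score factor 2(1 − r) |
|---|---|---|---|---|---|---|---|
| 0 | 1.00 | 0% | 0% | 110 | 0.378 SD | 0.440 SD | 2.0 |
| 0.2 | 0.96 | 4% | 2% | 115 | 0.370 SD | 0.431 SD | 1.6 |
| 0.3 | 0.91 | 9% | 5% | 121 | 0.360 SD | 0.420 SD | 1.4 |
| 0.5 | 0.75 | 25% | 13% | 147 | 0.327 SD | 0.381 SD | 1.0 |
| 0.6 | 0.64 | 36% | 20% | 172 | 0.302 SD | 0.352 SD | 0.8 |

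The 81-per-arm column shows the effect of incomplete return, using the pre-inflation size.

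Below r = 0.5 a change score is less precise than ignoring the start survey, while the adjusted model is never worse than either in this approximation. The three analyses are therefore not interchangeable.

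**3. Is the start survey a true baseline?** Section 2.3.4 gives the order as consent, sociodemographic and diagnostic data, randomisation, then equipment education, kit provision and creation of the patient's chart in the monitoring software before discharge. Section 2.3.1 says study-arm surveys are scheduled in that software, and places the first satisfaction survey only before the study period. The study-arm start survey could therefore be answered after the woman knows her allocation. The documents neither say that it is nor rule it out. A start score influenced by allocation would not be a safe covariate, so timing and adjustment have to be settled together.

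**The case against.** The strongest objection is that the plan excludes nothing. A reader might infer from section 2.4.2 that the planned Aim 3 analysis is an unadjusted two-sample test. The text does not support that: it assigns no test to satisfaction, and it permits the very regression proposed here. The baseline is unspecified, not ruled out. This stands, and it limits the point to missing specification plus a default that omits the start survey. It does not remove the point, because the regression sentence names neither outcome nor covariate.

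Second, a usable baseline score is not shown to exist. The two forms have different names and their content was not available. They may share few items, and a woman cannot rate a monitoring method she has not yet used. This also stands, and is why adjustment is limited to measures found in both surveys.

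Third, a reader might infer that precision is definitely lost. The size rests wholly on assumed correlations, and at r = 0 nothing is gained. If items are analysed as categories, the 1 − r² formula does not carry over directly.

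Fourth, a reader might infer bias from chance imbalance at the start. That is not so: under randomisation the unadjusted comparison is unbiased and its standard error already allows for chance imbalance. The issue is efficiency, for one of 13 secondary outcomes.

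**Conclusion.** The point holds as a minor one on precision and prespecification. Both arms are given a start and an end satisfaction survey, no section gives the start survey an analytic role, and the default two-group tests leave it out. Across assumed correlations from 0 to 0.6, adjustment would cut the variance by between 0% and 36%. At 110 per arm the detectable difference would move from 0.378 SD to as little as 0.302 SD.

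That range assumes a continuous score, a comparable measure on both forms, a start survey answered before allocation, equal arms and complete return. The documents settle none of the first three. The validity of the randomised comparison is not in question.

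**What to change.** 1. Have all women complete the start satisfaction survey at enrolment, alongside the sociodemographic data and before randomisation. If this cannot be done, do not use the start survey as a covariate.
2. Define the score and time point for secondary outcome 13, and list which scales or items appear on both forms.
3. Add to section 2.4.2 wording such as: for satisfaction scales or items measured at both start and end and scored as continuous, the end score will be analysed by linear regression on randomised arm and start score, and the adjusted difference reported with its 95% confidence interval. For categorical items, logistic or ordinal regression with the start response as covariate will be used.
4. State that end-only items, such as satisfaction with the monitoring method, will be compared without adjustment.

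The cost is moving one existing survey to the enrolment visit, a few sentences in the plan, and slightly more analysis work. No extra women or new instruments are needed.
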